9.3.3. Endometrial Biopsy

The protocol-specified endometrial biopsy procedure is performed at the Week 52 or Early Termination Visit in the extension study. Consensus readings were performed on all endometrial biopsies. Endometrial biopsies will be summarized according to primary diagnosis categories

from the consensus reading (Table 15). Endometrial biopsies performed in the parent studies and in the extension study at Week 52 or at the time of early termination will be summarized. Any repeat endometrial biopsies performed will also be summarized. All endometrial biopsy data will also be provided in a by-patient listing, including visits in both the parent study and extension study.

Table 15: Categories of Primary Diagnosis in Endometrial Biopsies

Category	Diagnosis
Atrophy/Inactive	
 Limited surface endometrium Atrophy Inactive
Proliferative	
 Weakly proliferative Active proliferative Disordered proliferative pattern
Mixed	
 Mixed proliferative and secretory
Secretory/Menstrual	
 Secretory cyclic type Secretory progesterational type (including stromal decidualization) Non secretory endometrium with breakdown Menstrual
Reactive/Inflammatory	
 Chronic Endometritis Acute Endometritis
Polyp	
 Polyp, atrophic Polyp, functional Polyp, hyperplastic Polyp, adenomyomatous Polyp, other
Hyperplasia	
 Hyperplasia, simple, without atypia Hyperplasia, complex, without atypia Hyperplasia, simple, with atypia Hyperplasia, complex, with atypia
Carcinoma	
 Malignant carcinoma Malignant sarcoma Malignant mixed Mullerian tumor Malignant, other
Other	
 Benign tumor Other non-physiologic epithelial changes

Other: cannot classify based on provided information	—
Inadequate	
 • No specimen in container: verified by pathologist • Tissue unsatisfactory for diagnosis: no endometrium present • Tissue unsatisfactory for diagnosis: too scant for reliable diagnosis

9.3.4. Bone Mineral Density

Corrected BMD data will be used for analysis as determined by the central radiology laboratory in the three prespecified anatomical locations: lumbar spine (L1–L4), total hip, and femoral neck.

BMD measured at Baseline, Week 12, Week 24, Week 36, and Week 52 visits will be summarized descriptively by parent study treatment group and each measured anatomical location for all patients in the Extension Safety population. Percentage changes from baseline along with 95% CIs of mean percentage changes also will be summarized by parent study treatment group and anatomical location. Mean percentage change from baseline with its corresponding 95% CI will be plotted by visit, parent study treatment group, and anatomical location.

A mixed-effects model with repeated measures will be used to assess BMD at 12, 24, 36, and 52 weeks. The model will be generated separately for each parent study treatment group and will have age at Baseline, visit, Baseline BMD value, stratification factors (geographic region and menstrual blood loss volume [as entered in the interactive web response system at the time of randomization]), race (African American versus Other), and BMI at Baseline as fixed effects using an unstructured variance-covariance matrix. Least square means on each anatomical location will be presented and plotted at each visit with associated 95% CIs. Categorical representation of percentage change from Baseline to 12, 24, 36, and 52 weeks of treatment will be presented by the number and proportion of patients who had BMD declines of $\leq 2\%$, $>2\%$ to 3% , $>3\%$ to 5% , $>5\%$ to 8% , and $>8\%$ by parent study treatment group and anatomical location. The 95% CIs will be provided for the respective proportions.

Categorical changes from Baseline in overall BMD (defined as lumbar spine and total hip) also will be assessed at 12, 24, 36, and 52 weeks. Femoral neck evaluates a smaller area of bone mass than the total hip and is prone to lower precision in the measurement (Leslie 2007; ISCD Official Positions 2015). Since femoral neck BMD may be associated with discordant readings compared with the total hip or lumbar spine due to technical considerations, it is not expected to add meaningful interpretation of overall BMD changes in response to treatment, though will be included for completeness.

Z-scores will be summarized by parent study treatment group, visit, and anatomical location with descriptive statistics including 95% CIs, and the number and percentage of patients with a Z-score < -2.0 will be presented by parent study treatment group, visit, and anatomical location.

BMD percentage changes from Baseline will also be summarized by intrinsic factors (eg, age, race, body mass index) and extrinsic factors (eg, geographic region). Subgroups will include, but will not be limited to, the subgroups outlined in [Table 16](#).

Table 16: Planned Subgroup Analyses

Subgroup Name	Subgroup Level
Geographic region	North America, Rest of World
Age category (years)	< 40, ≥ 40
Race	Black or African American, Not Black or African American
Ethnicity	Hispanic or Latino, Not Hispanic or Latino
BMI (kg/m ²) at Baseline	<30, ≥ 30

Abbreviations: BMI = body mass index.

Patients not enrolling in the MVT-601-035 study who had evidence of BMD loss of > 3% at the lumbar spine (L1 to L4) or total hip at their Week 52/EOT visit relative to the pre-treatment baseline measurement and patients who has evidence of BMD loss of > 2% at the lumbar spine (L1 to L4) or total hip at their EOT occurring prior to Week 36, underwent further testing and follow-up to evaluate recovery per the protocol. All available 6-month and 12-month post-treatment follow-up BMD data will be summarized to display the number and percent of patients who completed post-treatment follow-up, who met the threshold for recovery, and who did not meet the threshold for recovery.

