5.9. Prior and Concomitant Medications and Non-Drug Therapies

5.9.1. Prohibited Medications

Table 3 provides examples of prohibited drug categories; however, it is not a comprehensive list of all restricted medications. Drugs and drug classes in Table 3 are prohibited at any time during the study through the Follow-Up visit, except as noted in the table. Consult the medical monitor if there is any uncertainty regarding patient use of a particular drug or drug class.

Table 3: Prohibited Medications

Drug Class	Examples	Comments
Bisphosphonates	alendronate etidronate zoledronic acid	
GnRH Analogues	leuprolide acetate injection, also known as leuprorelin goserelin acetate injection	
Anti-Androgens	danazol	
Anti-convulsant drugs (specified)	phenobarbital carbamazepine phenytoin valproic acid primidone	All other anticonvulsants are allowed
Aromatase Inhibitors	anastrozole letrozole	
Progestins and progestin implants	dienogest norethindrone medroxyprogesterone cyproterone etonogestrel	
Estrogens	estradiol valerate conjugated estrogens ethynyl estradiol	

Drug Class	Examples	Comments
Hormonal Contraceptives, contraceptive patches and vaginal rings	combined or progestin only Nova Ring	
Selective Estrogen Receptor Modulators	raloxifene bazedoxifene lasofoxifene clomifene tamoxifen	
Selective Progesterone Receptor Modulators	mifepristone ulipristal acetate	
Over-the-counter and herbal products/teas with known hormonal activity	plant-based estrogen products “natural” thyroid supplements dihydroepiandrosterone (DHEA)	
Intrauterine Devices	Levonorgestrel system	
Bone Agents	calcitonin calcitriol ipriflavone teriparatide denosumab abaloparatide odanacatib romosozumab	Calcium and Vitamin D2 and Vitamin D3 (ergocalciferol and cholecalciferol) are allowed without restriction.
Anti-Coagulants/ Platelets/Fibrinolytics	warfarin clopedigril tranexamic acid vitamin k preparations factor Xa inhibitors	
Glucocorticoids	prednisolone or prednisone dexamethasone	Anticipated use (at screening) of systemic glucocorticoids at an oral prednisone-equivalent dose of more than 5 mg every other day during the study is prohibited. Note: topical, inhaled, intranasal, otic, ophthalmic, intraarticular, or intralesional subcutaneous are permitted without restriction. Short duration (≤ 21 days) higher-dose glucocorticoids required for acute events are permitted during the study.

Drug Class	Examples	Comments

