3.3. Safety Follow-Up Analyses

Patients who are not proceeding into study MVT-601-035 and who have endometrial hyperplasia or endometrial cancer on the endometrial biopsy should be treated as per standard of care and additional follow up should be evaluated and managed, as needed, by a gynecologist. In addition, they should undergo a repeat biopsy in 3 to 6 months after the Week 52/Early Termination and will be contacted to obtain information on procedures performed or treatments received (if any) for the biopsy findings through the time of the repeat biopsy. The repeat biopsy will be submitted to the central laboratory.

Patients who are not proceeding into study MVT-601-035 and who have a BMD loss of > 3% at the lumbar spine (L1–L4) or total hip relative to the Baseline measurement at their Week 52/Early Termination visit occurring on or after Week 36 will undergo a follow-up DXA scan 6 months (\pm 1 month) after discontinuation of study drug and will be contacted to obtain information about medications and conditions (eg, pregnancy, hyperparathyroidism, hypothyroidism, etc.) that might affect BMD through the time of the repeat DXA scan. Patients who have a BMD loss of > 2% at the lumbar spine (L1-L4) or total hip relative to the Baseline measurement at their Early Termination visit occurring prior to Week 36 will also undergo a follow-up DXA scan 6 months (\pm 1 month) after discontinuation of study drug. All follow-up DXA scans will be submitted for central reading.

Patients whose menses had not resumed as of the safety follow-up visit for unexplained reasons will be contacted by telephone to determine if menses have resumed.

Data collected during the additional safety follow-up period which is available at the time of database lock will be summarized and reported in the clinical study report. Complete data collected during the additional safety follow-up period will be summarized and reported in an addendum to the clinical study report.

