4.3.8. Visit Windows

Visit windows, which will be used to associate assessments with a scheduled visit, will be used only for summarizing data by visit. The windows for scheduled assessments are shown in [Table 2](#), [Table 3](#) (BMD), [Table 4](#) (electrocardiogram [ECG]), [Table 6](#) (UFS-QoL), and [Table 6](#) (transvaginal ultrasound and EQ-5D-5L) respectively. For safety assessments, the study day will be used to determine the associated visit window. There will be no separation of data from the parent and extension study. For example, if an assessment in the extension study falls in the Week 24 visit window, it will be summarized as Week 24.

If the results from more than one assessment are within a given visit window, the non-missing result from the assessment closest to the target date will be used. If two assessments are equally close to the target day, the earlier assessment will be used. For summaries of shift from Baseline in safety parameters, all values will be considered for these analyses.

Table 2: Visit Windows for Monthly Assessments

Visit	Start Day	Target Day	End Day
Week 4 ^a	1	29	43
Week 8	44	57	71
Week 12	72	85	99
Week 16	100	113	127
Week 20	128	141	155
Week 24	156	169	183
Week 28	184	197	211
Week 32	212	225	239
Week 36	240	253	267
Week 40	268	281	295
Week 44	296	309	323
Week 48	324	337	351
Week 52	352	365	Date of last dose + 6 ^b
Safety Follow-Up ^c	Date of last dose + 7 days	Date of last dose + 30 days	Date of last dose + 60 days

^a Start day of Week 4 for study day 1 includes only post-Baseline assessments that occurred after the first dose.

^b End day of Week 52 is date of last dose + 1 for patients entering the MVT-601-035 study.

^c The safety follow-up visit window will be restricted to assessments prior to the date of initiation of another investigational agent or hormonal therapy affecting the hypothalamic-pituitary-gonadal axis or surgical intervention for uterine fibroids.

Table 3: Visit Windows for Bone Mineral Density Assessments

Visit	Start Day	Target Day	End Day
Week 12	64	85	106
Week 24	148	169	196
Week 36	197	253	308
Week 52	309	365	421

Assessments will be excluded from analysis if they occur on or after the date of initiation of another investigational agent or hormonal therapy affecting the hypothalamic-pituitary-gonadal axis or surgical intervention for uterine fibroids. Assessments after date of last dose of extension study drug + 30 days will also be excluded from analysis.

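### The SAP's post-treatment bone-recovery count pools scans taken after other bone-active or hormonal treatment, so it cannot be read as recovery after stopping relugolix alone

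*SAP*

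**What the plan says.** **Recovery count.** SAP 9.3.4 concerns women who do not enter MVT-601-035 and whose bone loss at the spine or total hip exceeds a trigger: 3% at Week 52/EOT, or 2% if treatment ended before Week 36. For them, "All available 6-month and 12-month post-treatment follow-up BMD data will be summarized". The output is the number and percent who completed follow-up, "who met the threshold for recovery, and who did not meet the threshold for recovery". The section gives no exclusion, flag or stratum for treatment started after relugolix, and no value for the threshold.

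**History collected.** SAP 3.3 has sites obtain "information about medications and conditions (eg, pregnancy, hyperparathyroidism, hypothyroidism, etc.) that might affect BMD" up to the repeat scan. Protocol 6.6.2.6 asks for the same contact.

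**Drug restrictions.** Protocol 5.9.1 makes the classes in its Table 3 "prohibited at any time during the study through the Follow-Up visit, except as noted in the table". They include bisphosphonates, bone agents, selective estrogen receptor modulators, estrogens, progestins, hormonal contraceptives and GnRH analogues. Protocol 4.6 lets a woman begin hormonal contraception 4 weeks after her last dose if her cycle has returned.

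**Exclusion rule for BMD.** The note under SAP Table 3 (section 4.3.8) says "Assessments will be excluded from analysis if they occur on or after the date of initiation of another investigational agent or hormonal therapy", limited to therapy acting on the hypothalamic-pituitary-gonadal axis, and adds fibroid surgery. It continues: "Assessments after date of last dose of extension study drug + 30 days will also be excluded from analysis". The same section says visit windows "will be used only for summarizing data by visit".

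**The concern.** The rescanned women were selected because they lost bone, and they entered the parent studies with heavy menstrual bleeding. Some may start a bone agent, hormonal contraception or another hormonal treatment between stopping relugolix and the rescan. Such a drug can move BMD in either direction, as can a condition such as pregnancy. If those scans are pooled with scans from women who took nothing, the reported percentage mixes recovery after stopping relugolix with the effect of something else.

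Protocol Table 6 describes the bone loss as reversible, and this count is the analysis the SAP specifies for recovery. A reader of the study report will naturally take it as evidence on that statement. The plan already recognizes the confounder, since it tells sites to ask about it, but it does not say how the answers bear on the count.

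**Working it through.** The documents give no rate, sample size or precision for the recovery count, so there is no planned figure to reproduce. The check is of text and timing, followed by an illustration.

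**1. Does any rule remove the affected scans?** Taken alone, the hormonal-therapy clause in the SAP Table 3 note might seem to. It cannot. The same note drops every scan more than 30 days after the last dose, which would remove all 6- and 12-month scans. The windows are also confined to by-visit summaries. The recovery count is therefore governed only by SAP 9.3.4, which takes all available scans.

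**2. How long are the drugs unrestricted before the scan?** Inputs: Follow-Up visit about 30 days after last dose, window -3 to +18 days (Protocol Table 1); rescan at 6 ± 1 months (Protocol 6.6.2.6; SAP 3.3 counts from discontinuation); 1 month = 30.4375 days (SAP 4.1).

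- Follow-Up visit: 30 - 3 = day 27 to 30 + 18 = day 48.
- 6-month scan: 5 × 30.4375 = day 152.2 to 7 × 30.4375 = day 213.1.
- Shortest gap: 152.2 - 48 = about 104 days. Longest gap: 213.1 - 27 = about 186 days.
- Nominal 12-month scan (no window stated): 12 × 30.4375 = day 365.25, so 365.25 - 48 = about 317 to 365.25 - 27 = about 338 days.

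Protocol 6.3 brings the Follow-Up visit forward if hormonal therapy or a fibroid procedure is about to start, so for those women the unrestricted period can be longer.

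**3. Is the history used elsewhere?** SAP 5.5 counts a medication as concomitant only if exposure falls in the parent or extension treatment period, so drugs started afterwards are outside that summary. SAP 3.3 promises that data from the additional follow-up period will be summarized in the study report and an addendum. Neither links a woman's history to her recovery status.

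**4. What could pooling do?** Let t be the share of scanned women with intervening treatment, p the recovery rate without it and q the rate with it. The all-scan rate is (1 - t)p + tq, so it differs from p by t(q - p). The documents give none of these values; those below are assumptions.

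| t | p | q | All-scan rate | Difference from p (points) |
|---|---|---|---|---|
| 20% | 40% | 80% | 32 + 16 = 48% | +8 |
| 30% | 40% | 95% | 28 + 28.5 = 56.5% | +16.5 |
| 5% | 40% | 30% | 38 + 1.5 = 39.5% | -0.5 |
| 30% | 60% | 30% | 42 + 9 = 51% | -9 |

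Over t = 5% to 30%, p = 40% and 60%, and q = 60% to 95%, the difference is 0 to +16.5 points. With q = 30% it is -0.5 to -9 points. The sign depends on whether the intervening factor helps or hinders recovery.

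**5. On-treatment scans.** The SAP Table 3 note does not name bisphosphonates or bone agents, although Protocol Table 3 prohibits both. Assume 1% to 3% of women use one and gain 2% to 4% in BMD. The Week 52 mean then moves by 0.01 × 2 = 0.02 to 0.03 × 4 = 0.12 percentage points.

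**The case against.** - **The history is not discarded.** SAP 3.3 commits to summarizing the additional follow-up data, which would include the medication contact. This stands. The gap is that a separate summary does not show which recovered women had been treated.
- **Recovery is not a trial endpoint.** The BMD endpoint is percent change to Week 52, and SAP 2.2 plans no formal testing. The count is an uncontrolled description of a selected group. This also stands. A reader might infer that the trial fails to answer its reversibility question, but neither document lists recovery as an objective or endpoint, and the statement in Protocol Table 6 is a description of risk.
- **The direction is unknown.** A reader might infer that drug-induced gains are being counted as spontaneous recovery. The SAP does not call the recovery spontaneous, and an intervening drug or a condition such as pregnancy could equally lower BMD.
- **The size is unknown.** A reader might infer a shift as large as the treated share, for example 10 to 30 points if 10% to 30% were treated. That requires nobody to recover without treatment and everybody with it, or the reverse. The documents do not support either the uptake or those rates.
- **Untreated women are not a clean comparison group.** Women with worse loss may be the ones treated, so removing them could raise apparent recovery. This is a good reason not to make the untreated subset the sole main result.
- **On-treatment use is already controlled.** Bone agents are prohibited, anticipated use excludes a woman from entry, and use may be recorded as an important deviation (SAP 5.2). Keeping such scans is defensible, and the effect is small. What remains is an inconsistency in the exclusion note.

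**Conclusion.** The concern holds as a limit on interpretation. Followed as written, SAP 9.3.4 pools follow-up scans regardless of intervening bone-active or hormonal treatment, after roughly 104 to 186 days without restriction before the 6-month scan. The percentage cannot then be attributed to stopping relugolix alone. This rests on reading all available scans as having no exceptions; the SAP does not expressly say that treated women are included, but nothing removes them. It also rests on some women starting such treatment, which the protocol permits but does not quantify.

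The bias has no established sign, and its size cannot be computed from the documents. The +16.5 to -9 point span above is illustrative only. The omission of bone agents from the on-treatment exclusion note is a minor consistency matter, worth 0.02 to 0.12 percentage points on the Week 52 mean under assumed inputs.

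**What to change.** **In SAP 9.3.4:**

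- Use the contact data to flag each follow-up scan preceded by bone-active or hormonal treatment, or by another BMD-affecting condition of the kind named in SAP 3.3, such as pregnancy. List the qualifying drugs and conditions in advance.
- Report the recovery count for all scans, with the counts for unflagged and flagged scans beside it. State that the unflagged group is selected and smaller.
- Add a category for scans with no usable history. SAP 3.3 describes the contact for women above the 3% trigger and does not repeat it for those above the 2% trigger.
- State the recovery threshold or cite where it is defined. SAP 1 says the methods follow the parent studies, so a value may exist there.
- Say explicitly that the SAP Table 3 note does not apply to these scans.

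**In the SAP Table 3 (BMD) note:** extend the exclusion to scans on or after the start of a prohibited bisphosphonate or bone agent, leaving out the calcium and vitamin D that Protocol Table 3 allows. A sensitivity analysis would serve equally well.

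**Cost:** SAP wording and one more split in an existing table, with smaller numbers in each part. For women above the 3% trigger, the documents already require the history to be collected.

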APPENDIX 1: LIST OF PRE-DEFINED THRESHOLD IN SELECTED CHEMISTRY AND HEMATOLOGY TEST RESULTS

Chemistry Laboratory	
Liver Function	
ALT > ULN and < 3× ULN	Total BILI > ULN
ALT ≥ 3× ULN and < 5× ULN	Total BILI > 2× ULN
ALT ≥ 5× ULN and < 10× ULN	
ALT ≥ 10× ULN and < 20× ULN	ALT or AST ≥ 3× ULN and Total BILI > 2× ULN
ALT ≥ 20× ULN	ALT or AST ≥ 3× ULN and Total BILI > 2× ULN and ALP < 2× ULN
AST > ULN and < 3× ULN	GGT > ULN and < 3× ULN
AST ≥ 3× ULN and < 5× ULN	GGT ≥ 3× ULN and < 5× ULN
AST ≥ 5× ULN and < 10× ULN	GGT ≥ 5× ULN and < 10× ULN
AST ≥ 10× ULN and < 20× ULN	GGT ≥ 10× ULN and < 20× ULN
AST ≥ 20× ULN	GGT ≥ 20× ULN
ALT or AST > ULN and < 3× ULN	
ALT or AST ≥ 3× ULN and < 5× ULN	
ALT or AST ≥ 5× ULN and < 10× ULN	
ALT or AST ≥ 10× ULN and < 20× ULN	
ALT or AST ≥ 20× ULN	
Renal Function	
CR > 1.5 mg/dL and > BL	GFR < 15 mL/min per 1.73 m ²
CR > 50% increase from BL	GFR ≥ 15 - < 30 mL/min/1.73 m ²
	GFR ≥ 30 - < 60 mL/min min/1.73 m ²
	GFR ≥ 60 - < 90 mL/min min/1.73 m ²
	GFR ≥ 90 mL/min min/1.73 m ²

Chemistry Laboratory	
Metabolic Parameters	
Fasting Glucose	Highest Postbaseline Glucose
< 100 mg/dL at BL	Gluc \geq 200 mg/dL and > BL
< 100 mg/dL at Week 24	Gluc \geq 200 mg/dL and \geq 126 BL
\geq 100 - < 126 mg/dL at Week 24	Gluc \geq 500 mg/dL
\geq 126 mg/dL at Week 24	Gluc \geq 500 mg/dL and \geq 126 BL
\geq 100 - < 126 mg/dL at BL	Total CHOL > 200 mg/dL and > BL
< 100 mg/dL at Week 24	Total CHOL increase > 30 mg/dL from BL
\geq 100 - < 126 mg/dL at Week 24	
\geq 126 mg/dL at Week 24	HDL < LLN and < BL
	LDL > ULN and > BL
\geq 126 mg/dL at BL	TRIG > ULN and > BL
< 100 mg/dL at Week 24	
\geq 100 - < 126 mg/dL at Week 24	
\geq 126 mg/dL at Week 24	
Electrolytes and other Chemistry Parameters	
ALB < LLN and < BL	CK > 2 \times ULN and > BL
ALB > ULN and > BL	CK > 5 \times ULN and > BL
	CK > 10 \times ULN and > BL
ALP > 2 \times ULN and > BL	
ALP > 5 \times ULN and > BL	MG < LLN and < BL
ALP > 10 \times ULN and > BL	MG > ULN and > BL
CA < LLN and < BL	PHOS < LLN and < BL
CA > ULN and > BL	PHOS > ULN and > BL

K < LLN and < BL	NA < LLN and < BL
K > ULN and > BL	NA > ULN and > BL
Hematology Laboratory	
HCT < LLN and < BL	NEUT < LLN and < BL
HCT decrease ≥ 10 from BL	NEUT > ULN and > BL
HGB ≤ 10.5 g/dL and < BL	BASO < LLN and < BL
HGB decrease > 1 g/dL from BL	BASO > ULN and > BL
MCV < LLN and < BL	EOS < LLN and < BL
MCV > ULN and > BL	EOS > ULN and > BL
	EOS > 5% and > BL
WBC < LLN and < BL	
WBC > ULN and > BL	PLT < LLN and < BL
	PLT < $100 \times 10^9/L$ and < BL
LYM < LLN and < BL	PLT > ULN and > BL
LYM > ULN and > BL	
	HbA1c ≥ 6.5 and > BL
MONO < LLN and < BL	HbA1c increase > 1.0 from BL
MONO > ULN and > BL	

Abbreviations: ALB = albumin; ALP = alkaline phosphatase; ALT = alanine aminotransferase; AST = aspartate aminotransferase ; BL = baseline; BILI = bilirubin; CA = calcium; CHOL = cholesterol; CR = creatinine; EOS = eosinophils; GGT = gamma-glutamyl transferase; HCT = hematocrit; HDL = high-density lipoprotein; HbA1c = hemoglobin A1C; HGB = hemoglobin; K = potassium; LDL = low-density lipoprotein; LLN = lower limit of normal; LYM = lymphocytes; MG = magnesium; MCV = mean corpuscular volume; MONO = monocytes; NA = sodium; PHOS = phosphorus; PLT = platelets; ULN = upper limit of normal; WBC = while blood cells.
